2 ELIGIBILITY ASSESSMENT AND ENROLLMENT

2.1 ELIGIBILITY CRITERIA

2.1.1 Inclusion Criteria

2.1.1.1 Patients must have a documented diagnosis of multiple myeloma defined by the International Myeloma Working Group Criteria (IMWG)[\[3\]](#). Patients at initial diagnosis must have had a serum M-protein ≥ 3 g/dL and/or bone marrow plasma cells $\geq 10\%$, and at least one of the following:

- Anemia: Hemoglobin ≤ 10 g/dL, or
- Renal failure: serum creatinine ≥ 2.0 mg/dL, or
- Hypercalcemia: Ca ≥ 10.5 mg/dL, or
- Lytic bone lesions on X-ray, CT, or PET/CT, or
- ≥ 2 focal lesions on spinal MRI, or
- $\geq 60\%$ bone marrow plasma cells, or
- Involved/un-involved serum free light chain ratio ≥ 100

2.1.1.2 Have at least one extramedullary plasmacytoma or lytic lesion which at the discretion of the investigators is amenable to and clinically indicated for localized radiation therapy

2.1.1.3 Must have *Relapsed* or *Relapsed and Refractory* Multiple Myeloma. Patients must have documented evidence of progressive disease (PD) as defined by the IMWG criteria on or after their last regimen and must have achieved a minimal response (MR) or better to at least one prior regimen. Definitions by the IMWG:[\[93\]](#)

- Relapsed and refractory: disease that is nonresponsive while on salvage therapy or progresses within 60 days of last therapy in patients who have achieved minor response (MR) or better
- Relapsed: disease that progresses and requires the initiation of salvage therapy but does not meet criteria for either *primary refractory* or *relapsed and refractory* MM categories

2.1.1.4 Patients must have been previously treated for MM and be refractory to, not a candidate for (ineligible), or intolerant of available therapeutic regimens known to provide clinical benefit including immunomodulatory (IMiD), proteasome inhibitor, and anti-CD38 monoclonal antibody-based treatments.

2.1.1.5 Documented measurable disease within the 4 weeks prior to registration defined by any one of the following:

- Monoclonal Bone marrow plasma cells $\geq 5\%$
- Serum monoclonal protein ≥ 0.2 g/dl
- Urine monoclonal protein > 200 mg/24 hour
- Serum immunoglobulin free light chain > 10 mg/dL AND abnormal kappa/lambda ratio
- A measurable lesion on PET/CT or MRI

2.1.1.6 Be ≥ 18 years of age on day of signing informed consent

Note: The estimated 2017 US incidence of MM of patients under the age of 20 is 0.0%; therefore, children are excluded from enrollment in this study. [2]

2.1.1.7 ECOG performance status ≤ 2 ([Appendix A](#))

2.1.1.8 Adequate organ function as evidenced by the following laboratory parameters:

• Absolute neutrophil count (ANC)	≥ 1000 /mcL
• Platelets	$\geq 75,000$ / mcL
• Hemoglobin	≥ 8 g/dL (transfusions permitted)
• Serum creatinine OR Measured CrCl or eGFR by CKD-EPI formula may be used to estimate CrCl/eGFR	≤ 1.5 X ULN (except if due to myeloma) OR ≥ 30 mL/min/1.73 m ² for subject with creatinine levels > 1.5 X ULN
• Serum total bilirubin	≤ 1.5 X ULN OR Direct bilirubin \leq ULN for patients with total bilirubin levels > 1.5 ULN (except if due to myeloma)
• AST (SGOT) and ALT (SGPT)	≤ 2.5 X ULN (except if due to myeloma)

2.1.1.9 The effects of avelumab on the developing human fetus are unknown, however, given the known role of PD-1/PD-L1 in maintaining the maternal/fetal tolerance, avelumab can be expected to have an adverse effect on pregnancy, including embryo-lethality. Women of child-bearing potential (WOCBP) and men must agree to use highly effective contraception (such as implants, injectables, combined oral contraceptives, IUDs, sexual abstinence or vasectomised partner) prior to study entry and for the duration of study treatment, and for at least 30 days after the last dose of avelumab. Should a woman become pregnant or suspect she is pregnant while she or her partner is participating in this study, she should inform her treating physician immediately.
NOTE: WOCBP is defined as any female who has experienced menarche and who has not undergone successful surgical sterilization or who is not postmenopausal.

2.1.1.10 Negative serum or urine pregnancy test at screening for WOCBP.

2.1.1.11 Ability of patient to understand and the willingness to sign a written informed consent document

2.1.2 Exclusion Criteria

2.1.2.1 Patients with clinically unstable lesions (e.g., impending cord compression) where a delay in receiving XRT would be detrimental are not eligible

2.1.2.2 Current or prior anti-cancer treatment prior to the first dose of avelumab as defined below:

- Chemotherapy, targeted small molecule therapy, or other anti-cancer treatment not otherwise specified below within 2 weeks
- Radiation therapy within 2 weeks
- Anti-cancer monoclonal antibody (mAb) treatment within 4 weeks
- Use of an investigational agent (e.g., biologic, drug, or other) within 4 weeks
- Allogeneic stem cell transplant

2.1.2.3 No autoimmune disease, as follows:

- Active (acute or chronic) autoimmune disease that might deteriorate when receiving an immuno-stimulatory agent. Patients with type I diabetes, vitiligo, psoriasis, or hypo- or hyperthyroid diseases not requiring immunosuppressive treatment may be eligible.
- History of serious autoimmune-related disorders including immune colitis, inflammatory bowel disease, pneumonitis, or pulmonary fibrosis whether drug-mediated or not.

2.1.2.4 Current use of immunosuppressive medication, EXCEPT for the following:

- Intranasal, inhaled, topical steroids, or local steroid injection (e.g., intra-articular injection)
- Systemic corticosteroids at physiologic doses
- Steroids as premedication for hypersensitivity reactions (e.g., CT scan premedication)

2.1.2.5 Uncontrolled intercurrent illness including, but not limited to the following that may limit interpretation of results or that could increase risk to the patient in the judgment of the investigator:

- Patients with a positive hepatitis B core antibody [HBcAb] and negative surface antigen (HBsAg) may be included if HBV DNA is undetectable
- Patients who are positive for HCV antibody must be negative for HCV by polymerase chain reaction (PCR) to be eligible for study participation
- Known acquired immunodeficiency syndrome (AIDS). Controlled and stable HIV positivity is allowed
- Prior organ transplantation including allogeneic stem-cell transplantation
- Clinically significant cardiovascular disease: cerebral vascular accident/stroke (<

6 months prior to enrollment), myocardial infarction (< 6 months prior to enrollment), unstable angina, congestive heart failure (\geq New York Heart Association Classification Class III), or serious cardiac arrhythmia requiring medication. Mild arrhythmias, e.g. stable atrial fibrillation, may be allowed at the discretion of the investigator

- Active infection requiring systemic therapy (minor infections may be allowed at the discretion of the investigator)
- Known mental or physical illness that would interfere with cooperation with the requirements of the trial or confound the results or interpretation of the results of the trial and, in the opinion of the treating investigator, would make the patient inappropriate for entry into the study.

2.1.2.6 Persisting toxicity related to prior therapy (Grade > 1); however, alopecia, sensory neuropathy Grade \leq 2, or other Grade \leq 2 not constituting a safety risk based on investigator's judgment are acceptable.

2.1.2.7 Vaccination with live vaccines within 4 weeks of the first dose of avelumab and while on study is prohibited (inactivated vaccines may be administered).

2.1.2.8 Pregnant or lactating females. Because there is an unknown but potential risk for adverse events in nursing infants, on-study breastfeeding is not allowed.

2.1.2.9 History of allergic reactions or hypersensitivity to avelumab or any component in its formulations, including known severe hypersensitivity reactions to monoclonal antibodies (Grade \geq 3) unless felt to be in the best interests of the patient at the discretion of the investigator.

2.1.2.10 Known additional malignancy that is symptomatic or requires active systemic treatment (at the discretion of the PI, exceptions may be made if in the best interest of the patient).

2.1.2.11 Other severe acute or chronic medical conditions including immune colitis, inflammatory bowel disease, immune pneumonitis, pulmonary fibrosis or psychiatric conditions including recent (within the past year) or active suicidal ideation or behavior; or laboratory abnormalities that may increase the risk associated with study participation or study treatment administration or may interfere with the interpretation of study results and, in the judgment of the investigator, would make the patient inappropriate for entry into this study.

2.1.3 Recruitment Strategies

Study participants will be recruited from the population of patients screened in the lymphoid malignancies clinic of the National Institutes of Health. These will include both referrals from outside physicians as well as patient self-referrals. Of note, our outside physician referral network has a high representation of minorities.

This study will be posted on NIH websites and on NIH social media forums. Study-specific public service announcements and informational fliers will be used for recruitment activities. All information to be posted or distributed publicly will be submitted to the IRB for review and approval in advance of use.

2.2 SCREENING EVALUATION

2.2.1 Screening activities performed prior to obtaining informed consent

Minimal risk activities that may be performed before the subject has signed a consent include the following:

- Email, written, in person or telephone communications with prospective subjects
- Review of existing medical records to include H&P, laboratory studies, etc.
- Review of existing MRI, x-ray, or CT images
- Review of existing photographs or videos
- Review of existing pathology specimens/reports from a specimen obtained for diagnostic purposes

2.2.2 Screening activities performed after a consent for screening has been signed

The following activities will be performed only after the subject has signed the study consent **or** the consent for study 01-C-0129 (provided the procedure is permitted on that study) on which screening activities will be performed. Assessments performed at outside facilities or on another NIH protocol within the timeframes below may also be used to determine eligibility once a patient has signed the consent.

NOTE: Assessments and procedures to confirm study eligibility should be completed within 28 days prior to registration (unless otherwise noted).

2.2.3 Clinical Evaluations

- Confirmation of disease diagnosis (i.e., review of pathology and/or hematopathology, as required)
- Disease history, including: diagnosis, treatment (e.g., systemic treatments, radiation and surgeries), status, and significant prior/ongoing side effects and symptoms
- Complete medical history, including: all active conditions considered to be clinically significant by the treating investigator
- Physical examination, including: height (screening only), weight, vital signs (i.e., temperature, pulse, respiratory rate, and blood pressure); review of concomitant medications and symptoms/side effects; and, assessment of performance status

2.2.4 Laboratory Evaluations

NOTE: Results from outside NIH are accepted.

- CBC with differential
- Chemistry panels: Acute Care (sodium, potassium, chloride, CO₂, glucose, BUN, creatinine), Mineral (serum calcium, phosphate, magnesium and albumin) and Hepatic (alkaline phosphatase, ALT, AST, total and direct bilirubin) and 24-hour urine creatinine clearance (if needed to measure CrCl in cases where serum creatinine > 1.5 X ULN)
- Thyroid function tests, including: thyroid stimulating hormone (TSH), total triiodothyronine (T3), free thyroxine (T4)

- Hepatitis B surface antigen (HBsAg), Hepatitis B core antibody, Hepatitis C antibody (HCV) [qualitative] (within 3 months). If Anti HCV is positive, will follow with HCV RNA PCR
- Anti-HIV-1/2 Antibody (within 3 months)
- Urine and/or serum HCG in WOCBP (within 3 days prior to enrollment and initiation of study therapy)
- Uric acid, LDH, and Beta-2 Microglobulin
- Serum protein electrophoresis (SPEP) and immunofixation to assess for presence and quantity of monoclonal protein (M-protein)
- Random urine sample for protein electrophoresis (UPEP) and immunofixation to assess for monoclonal protein in the urine (Bence-Jones proteinuria). Collect a 24 hour urine sample if patient's serum monoclonal protein is ≤ 0.2 g/dL.
- Serum free light-chain studies
- Quantitative immunoglobulins

2.2.5 Imaging Studies

NOTE: For the purposes of screening, outside radiology may be used, however, a baseline performed at NIH will be needed.

- ^{18}F -FDG PET/CT to confirm extramedullary disease and/or lytic lesions (in certain scenarios, at the discretion of the investigator, a chest, abdomen and pelvis CT or MRI without contrast may substitute).

2.2.6 Other Procedures

- 12-lead EKG
- Optional: Bone marrow biopsy for screening may be done if patient does not have measurable disease otherwise (see eligibility). If done for screening/eligibility purposes, it does not have to be repeated as a baseline measure.

2.3 PARTICIPANT REGISTRATION AND STATUS UPDATE PROCEDURES

Registration and status updates (e.g., when a participant is taken off protocol therapy and when a participant is taken off-study) will take place per CCR SOP ADCR-2, CCR Participant Registration & Status Updates found [here](#).

2.3.1 Treatment Assignment Procedures

2.3.1.1 Cohorts

Number	Name	Description
1	RRMM	Patients with relapsed/refractory multiple myeloma (RRMM), including at least one extramedullary plasmacytoma or lytic lesion amenable to and clinically indicated for localized radiation therapy

2.3.1.2 Arms

Number	Name	Description
1	Experimental therapy	Avelumab 800 mg IV every two weeks in combination with radiation therapy

2.3.1.3 Arm Assignment

Single arm/group assignment; open-label and non-randomized (i.e., subjects in Cohort 1 directly assigned to Arm 1).

2.4 BASELINE EVALUATION

The following should be performed within 28 days prior to the first dose of avelumab unless otherwise noted; tests performed as part of screening do not need to be repeated if they were performed within the specified window prior to the first dose of avelumab.

NOTE: Results from an outside NIH institution are accepted at the discretion of the investigator.

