3.7 STUDY CALENDAR

Procedure	Screening ¹	Baseline ²		Treatment Cycles ³						Disease Evaluations ⁴	End of Treatment ⁵	Post-Treatment Follow-Up		
				Cycle 1				Cycle 2				Cycle 3+	Safety ⁶	Follow-Up (Prior to PD) ⁷
				1	8	15	22	1	15 ⁸			1		
Study Cycle Day: (1 cycle = 28 days or 4 weeks)														
Physical Exam (including, history, vitals, weight, and height [screening only]); ECOG PS	X	X*	X	X	X	X	X	X		X	X	X		
Confirmation of Diagnosis	X													
CBC with Differential	X	X*	X	X	X	X	X	X		X	X	X		
Reticulocyte Count		X*	X	X	X	X	X	X		X	X	X		
Chemistry Panels (i.e., Acute care, Mineral, Hepatic)	X	X*	X	X	X	X	X	X		X	X	X		
LDH, Uric Acid, Total Protein		X*	X	X	X	X	X	X		X	X	X		
PT/INR and aPTT		X												
Thyroid Function (i.e., TSH, T3, T4)	X	X*				X	X	X		X	X	X		
Urinalysis			X	X	X	X	X	X		X	X	X		
Pregnancy Test (urine/serum HCG; WOCBP) ⁹	X	X				X		X						
Hepatitis B and C Testing (within 3 months)	X													
HIV Antibody Testing (within 3 months)	X													
Myeloma Tests ¹⁰	X	X*				X	X	X		X	X	X		
12-lead EKG	X													
T/B/NK cell subsets		X	X			X	X	X		X	X	X		
Skeletal Survey		X					X [#]		X	(X)	X	X		
¹⁸ F-FDG-PET/CT Scan ¹¹ & DW MRI	X	X					X [#]	X ¹¹	X	(X)	X	X		
Radiation Therapy Imaging		X												
Bone Marrow Aspiration/Biopsy ¹²		X					X [#]		X	(X)	(X)			
Symptoms/Toxicity Assessment, Concomitant Medication Review	X	X	X	X	X	X	X	X		X	X	X		
Research Samples ^{#13}		X	See Table in Section 5.1											
PROs/Questionnaires [#]		X					X			X		X		
Survival												X (Post-PD)		

(X) = Optional. **NOTE:** Other tests/assessments may be performed at the discretion of the investigator as clinically indicated.

[#]See Section 5, Correlative Studies for Research, for additional information on the research blood, urine, bone marrow sampling, and questionnaires..

¹ Screening evaluations should be performed within 28 days, with the following exceptions: Confirmation of diagnosis (no time limit); HIV antibody, Hepatitis B surface antigen and Hepatitis C antibody (within 3 months). **NOTE:** Screening tests performed within the time frame for baseline do not need to be repeated.

² Baseline evaluations should be performed within 28 days prior to first dose of avelumab unless otherwise noted, tests performed as part of screening do not need to be repeated if performed within the specified window. **NOTE:** Items marked with an asterick (*) are required within 14 days prior to first dose.

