10 STATISTICAL CONSIDERATIONS

10.1 STUDY ENDPOINTS

- Primary Endpoint:
 - The primary endpoint of this study is to determine the overall response rate (ORR) in patients with multiple myeloma treated with avelumab and irradiation.
- Secondary Endpoints:
 - The secondary endpoints are to determine:
 - Complete Response (CR) rate and Minimal Residual Disease (MRD) negative CR rate,
 - Reductions in bone marrow (BM) and peripheral blood (PB) plasmacytosis,
 - Radiographic reduction in size, and/or FDG avidity (PET/CT) of extramedullary lesions,

- Radiographic reduction in size, and/or FDG avidity (PET/CT) of non-irradiated extramedullary lesions (abscopal effect)
- Progression-free survival (PFS)
- Overall survival (OS)
- All Grade, Grade 3-4, and serious adverse events, and
- ORR post cycle 1 (prior to XRT)
- Exploratory Endpoints
 - Correlative Studies may be performed in select patients where adequate samples are available:
 - Peripheral blood mononuclear cells (PBMCs):
 - Changes in 123 immune subsets including CD4 and CD8 T cells, natural killer [NK] cells, NK-T cells, regulatory T cells [Tregs], myeloid-derived suppressor cells [MDSCs], and dendritic cells and 114 refined subsets relating to maturation/function using multicolor flow cytometry
 - Changes in the function of select immune cell subsets (e.g. CD4 and CD8 effector T cells, NK cells, Tregs, and MDSCs)
 - Changes in tumor antigen specific T cells (e.g. brachyury, MUC1, and CEA) using intracellular cytokine staining for IFN γ , TNF, and IL2 and the degranulation marker CD107a
 - Changes in T-cell clonality score using adaptive biotechnologies TCRseq assay
 - Changes in inflammatory gene signature using Nanostring's nCounter Human PanCancer Immune Profiling Panel
 - Plasma/Serum:
 - Changes in sCD27, sCD40L
 - Changes in cytokines (IFN- γ , IL-10, IL-12, IL-2, IL-4, etc.), chemokines, antibodies, tumor-associated antigens, and/or other markers
 - Changes in VDJ copy number of MM clones
 - Bone Marrow:
 - Changes in immune subsets
 - Changes in VDJ copy number of MM clones
 - DNA genetic alterations and TMB of MM cells

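### Baseline PET/CT, DW-MRI and marrow may come before permitted prior treatment, in a gap of up to about 14 days, which exposes mainly the descriptive lesion and marrow endpoints to carry-over

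*Combined protocol and SAP*

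**What the plan says.** **Baseline window.** The default in protocol Section 2.4 is: "The following should be performed within 28 days prior to the first dose of avelumab unless otherwise noted". Sections 2.4.3 (marrow) and 2.4.4 (PET/CT, DW-MRI, skeletal survey) set nothing shorter. In the study calendar (3.7) the asterisked items "are required within 14 days prior to first dose". The myeloma tests carry the asterisk at baseline; imaging and marrow do not. Section 2.4.2 agrees, placing serum and urine electrophoresis and free light chains in the 14-day group.

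**Washout.** Section 2.1.2.2 counts back from the same date: "Current or prior anti-cancer treatment prior to the first dose of avelumab as defined below". For external beam treatment the limit is "Radiation therapy within 2 weeks". Chemotherapy and small molecules share a line that ends "or other anti-cancer treatment not otherwise specified below within 2 weeks". Anti-cancer antibodies and investigational agents have 4 weeks.

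**Marrow taken at screening.** Section 2.2.6 says of such a marrow: "If done for screening/eligibility purposes, it does not have to be repeated as a baseline measure". Screening assessments "should be completed within 28 days prior to registration" (2.2.2), so they are anchored to registration and not to the first dose.

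**Endpoints.** Section 10.4.3 reports percent change from baseline in marrow and blood plasma cells, and in the size or FDG avidity of extramedullary lesions. Section 10.1 adds the reduction "of non-irradiated extramedullary lesions (abscopal effect").

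**The concern.** A change-from-baseline measure isolates study treatment only if no other active treatment falls between the baseline and the first dose. The windows do not secure this for imaging and marrow. A patient can have a baseline PET/CT, then receive palliative radiotherapy or a last course of chemotherapy, observe the 2-week washout and start avelumab, all within the rules. Shrinkage due to the earlier treatment would then be credited to the combination. There is no control arm to reveal it.

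The abscopal endpoint deserves most care, because shrinkage away from the study radiation field is the mechanism that the trial sets out to test (1.2.9).

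**Working it through.** **1. The gap.** All windows count back from the first avelumab dose. Gap = baseline window - washout.

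| Baseline item | Baseline window | Prior treatment | Washout | Gap |
|---|---|---|---|---|
| PET/CT, DW-MRI, marrow | 28 days | Chemotherapy, small molecules, radiotherapy | 14 days | 28 - 14 = 14 days |
| PET/CT, DW-MRI, marrow | 28 days | Antibodies, investigational agents | 28 days | 28 - 28 = 0 |
| M-protein, FLC | 14 days | Chemotherapy, small molecules, radiotherapy | 14 days | 14 - 14 = 0 |

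The mismatch is specific to imaging and marrow, and to treatments with the 2-week washout. For a screening marrow the gap could be longer, because 2.2.6 waives the repeat and 2.2.2 counts from registration.

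**2. Whether another passage closes it.** None does. No section requires the baseline scan or marrow to follow the last prior treatment. The bar on other myeloma therapy in 4.2 applies during trial treatment. The rule that baseline imaging be done at NIH (2.2.5, 2.4.4) fixes the place, not the order.

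**3. A compliant example.** PET/CT on day -27; radiotherapy to lesion A on days -24 to -20; first dose on day 1. The last fraction falls 20 days before the first dose, outside the 14-day exclusion. Cycle 2 Day 15 is study day 28 + 15 = 43. With no day 0, that scan falls 27 + 42 = 69 days after baseline and 20 + 42 = 62 days after the last off-study fraction. The change in lesion A would include the effect of that radiotherapy.

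**4. Reach into the primary endpoint.** Under Appendix F, partial response needs the M-protein criteria, or the FLC criterion when serum and urine M-protein are unmeasurable. Both rest on the protected 14-day baseline. A reduction of at least 50% in soft tissue plasmacytomas, if present, is required on top. Two narrow routes remain:

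- a patient who meets the M-protein or FLC criteria passes the plasmacytoma condition only because of earlier treatment;
- a patient with no measurable serum, urine or FLC disease is assessed by marrow, which requires at least 30% plasma cells at baseline.

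The marrow limb of complete response is an absolute level below 5%, not a change.

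**5. Sensitivity of the ORR decision.** The design in 10.2 reproduces. Early termination under the null is 0.95^13 = 0.513, as stated. The chance of declaring success at response rate p is the sum over x = 1 to 13 of P(X1 = x) × P(X2 ≥ max(0, 4 - x)), with X1 ~ Bin(13, p) and X2 ~ Bin(14, p). This gives 0.0416 at p = 0.05 and 0.801 at p = 0.20.

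The documents give no carry-over rate. As an assumption only, adding 1, 2, 3 or 5 percentage points to the 5% null would raise 0.042 to 0.072, 0.111, 0.159 or 0.271. The decision is sensitive to small additions, but nothing in the documents places the trial in this range, and the routes in step 4 are narrow.

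**The case against.** Several safeguards stand, and they rule out stronger readings that a reader might infer.

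- **That one false response could open stage 2 (1 of 13).** The example in step 3 yields no partial response in a patient with measurable M-protein or FLC. Plasmacytoma shrinkage is a further hurdle for partial response, not a way round the M-protein or FLC criteria.
- **That late effects of systemic therapy are freely counted.** Section 2.1.1.3 requires documented progression on or after the last regimen. A regimen given in the gap would be the last regimen. This limits systemic carry-over, though it does not require the scan or marrow to come after treatment and does not deal with local radiotherapy given after the scan.
- **That a lesion irradiated before the study would be scored as abscopal.** Read plainly, a lesion that has had radiotherapy is not non-irradiated. Radiation history is taken at screening (2.2.3) and interim history at baseline (2.4.1), so the analyst can know. The text does not spell the rule out, but it does not support the contrary.
- **That the bias always favours activity.** These patients have progressing disease. Untreated growth between an early scan and the first dose counts against the drug.
- **That the frequency is known.** The figure of about a third in 1.2.3 is lifetime use of radiotherapy. A guess of 5-10%, or about 1 to 3 of 27 patients (0.05 × 27 = 1.35; 0.10 × 27 = 2.7), has no basis in the documents, and patients treated in the gap are not the same as false responders.

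The gap may also be used rarely. Baseline imaging is done at NIH, unstable lesions that cannot wait are excluded (2.1.2.1), and 3.3.3 intends to treat on study the lesions that clinically require it. None of this removes the point that the windows, followed exactly, permit a pre-treatment baseline.

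**Conclusion.** The mismatch is real: up to about 14 days in which chemotherapy, small-molecule therapy or radiotherapy may follow the baseline PET/CT, DW-MRI or marrow. It bears mainly on descriptive secondary endpoints that carry no test, and only narrowly on the ORR. Severity is minor to moderate.

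The 14 days is the maximum that the wording allows for a baseline inside the 28-day window. How many patients would fall in it, and the net direction of bias across patients, cannot be settled from the documents. The point is worth acting on because a single-arm trial cannot detect such carry-over afterwards and the remedy is cheap.

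**What to change.** 1. In 2.4, require baseline PET/CT, DW-MRI and marrow to be obtained after the last dose or fraction of prior anti-myeloma treatment and within 28 days before the first avelumab dose. Apply the same condition to a screening marrow used as baseline under 2.2.6. Anyone who meets the existing 2-week washout still has about two weeks to schedule these assessments.
2. Where treatment was nevertheless given after the baseline, repeat the imaging, or leave the affected lesion or marrow value out of the change-from-baseline analyses. No extra biopsy is then needed.
3. In 10.4.3, state that the abscopal set excludes lesions irradiated after the baseline scan or shortly before enrollment, with the look-back period written down in advance, using the radiation history already collected under 2.2.3.

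The cost is a few sentences, slightly later scheduling and an occasional repeat scan. Washouts, treatment and the 27-patient design are unchanged.
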